[figure not shown]

Study Title	
Assessment of Cutting-Balloon Angioplasty with Novel Bioabsorbable Polymer-Coated, Everolimus-Eluting Stent in the Treatment of Calcified Coronary Lesions Guided by Intravascular Ultrasound: Study Design and Protocol

Study Title (Short Description)	
CUPID trial

Principle Investigator	
[name]., PhD.

Institution Name & Location	
SoonChunHyang University Hospital [name]

Contact information	
Email: [contact] [contact] [contact]

1. Study protocol

Novel cutting balloon prospective, randomized, open-label, multi-center study

This clinical trial is designed as a prospective, observational, open-label, multi-center trial that will investigate the noninferiority of cutting balloon pre-dilatation compared with NC-balloon pre-dilatation in the treatment of calcified lesion who underwent bioabsorbable polymer-coated, everolimus-eluting coronary stent implantation.

Planned number of sites: 5 institutions in South Korea

1. SoonChunHyang University Hospital, Bucheon
2. SoonChunHyang University Hospital, Cheonan
3. Eulji Medical Center, Eulji University, Daejeon
4. Seoul St.Mary's Hospital, Seoul
5. Hanil General Hospital, Seoul

2. Study Outcomes

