5.2. Secondary endpoint: comparing the clinical outcomes

- ① MACE (major adverse cardiac events): composite of death, MI, TVR at 1yr follow-up
- ② TLR (target lesion revascularization) at 1yr follow-up
- ③ Procedure time, the total amount of contrast, and the number of balloons

3. Analysis plan

- 6.1. Study period: 24 months
- 6.2. Enrollment: 12 months
- 6.3. Follow-up: 12 months
- 6.4. Analysis and result report: 2 months

4. Sample size calculation for the primary analysis

4.1. Hypothesis:

This trial is a 1:1 matched comparative cohort clinical trial, with patients being assigned to either the cutting balloon or the NC balloon group (1: 1 ratio) during the study period. It will test the noninferiority of a strategy of cutting balloon pre-dilatation compared with NC balloon pre-dilatation in the treatment of calcified coronary lesion. minimal CSA at the calcium site assessed by IVUS is the primary endpoint. Limited similar clinical trials on cutting balloon for the treatment of de novo various degree calcified coronary lesions have achieved differing results. The result of a previous study that investigates the efficacy of cutting balloon indicates that the mean CSA after cutting balloon treatment for native coronary artery disease are 6.26mm and 5.03 mm in the NC balloon group (18). We hypothesize that stent implantation after the cutting balloon pre-dilatation will not be inferior to pre-dilatation with NC balloon for the treatment of de novo calcified coronary lesions. Using double-sided inspection, $\alpha = 0.05$ and $\beta = 0.2$, and considering the expected loss to follow-up of 20%, the number of cases to be included should be at least 250. Therefore, we aim for 125 cases for each group. Nevertheless, the sample size proposed was 250 patients in each group to further increase the power and account for possible protocol deviation.

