4.2. Assumption

Data for all endpoints will be evaluated using an intention-to-treat analysis. All data will be expressed as mean \pm standard deviation. The unpaired Student's t-test and Mann-Whitney U test will be used to compare continuous variables. Categorical variables will be compared using the chi-square and Fisher's exact tests. All time-to-event outcomes of MACEs will be summarized using Kaplan-Meier survival estimates and compared between the two groups using log-rank tests. $p < 0.05$ is considered statistically significant. All statistical analyses will be performed using SPSS software (version 20.0, SPSS Inc., Chicago, IL, USA).

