Coronary angiography will be digitally recorded at baseline and immediately after the procedure (post-balloon and post-stenting) and assessed offline in the angiographic core laboratory. The quantitative coronary angiographic analysis will be performed using an automated edge-detection algorithm (CAAS-5; Pie-Medical, Best, Netherlands) with conventional methods by independent interventional cardiologists who are blinded to the type of balloon used, treatment outcomes, and IVUS analysis. All measurements will be performed using cineangiograms recorded after the intracoronary injection of nitroglycerin. The interpolated reference diameter will be considered as the reference segment diameter. The lesion length is defined as the distance from the proximal shoulder to the distal shoulder at the lesion site. Standard qualitative and quantitative analyses and definitions will be used for quantitative coronary angiography (QCA) (qca 1, 2 references).

5.3. IVUS procedure and analysis:

After regular coronary angiography, IVUS will be performed at baseline (before pre-dilatation) and repeated immediately after stent implantation in all cases. IVUS will be performed using an OptiCross 60 MHz (Scientific Corporation, Maple Grove, MN, USA). After intracoronary injection of nitroglycerin, the IVUS catheter will be carefully advanced distal to the culprit lesion under fluoroscopic guidance and then withdrawn automatically at 0.5 mm/s to perform the imaging sequence, which begins 20 mm distal to the culprit lesion and ends at the aorto-

ostial junction. IVUS imaging will be recorded on the compact disc for offline analysis by a single experienced observer who is unaware of the clinical and angiographic information. IVUS measurements will be performed in accordance with the American College of Cardiology Clinical Expert Consensus Document on the Standards for Acquisition, Measurement, and Reporting of Intravascular Ultrasound Studies. The ischemia-related vessel is identified as narrow ($\geq 70\%$) using angiography. The culprit lesion site selected for analysis is the image slice with the lowest luminal cross-sectional area (CSA). The proximal and the distal reference segments are defined as the most normal-looking cross-sections within the same arterial segment, typically ≤ 10 mm from the lesion, but before any large side branch.

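### The plan describes allocation as both random and non-random, with no allocation procedure, no matching variables and no adjusted analysis

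*Combined protocol and SAP*

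**What the plan says.** Three places in the current text describe how the study is built.

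- Section 1, opening line: "Novel cutting balloon prospective, randomized, open-label, multi-center study".
- Section 1, next sentence: "This clinical trial is designed as a prospective, observational, open-label, multi-center trial".
- Section 4.1 (Hypothesis), first sentence: "This trial is a 1:1 matched comparative cohort clinical trial, with patients being assigned to either the cutting balloon or the NC balloon group", at a ratio of 1:1.

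The ratio, and the 125 per group in section 4.3, are the only details of allocation. The document gives no sequence generation, concealment or stratification, and no matching variables or algorithm.

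Section 4.2 (Assumption) sets the analysis: "Data for all endpoints will be evaluated using an intention-to-treat analysis". The primary endpoint, minimal stent cross-sectional area (CSA) at the calcium site, is continuous. For such variables the section names the unpaired Student test and its rank counterpart: "t-test and Mann-Whitney U test will be used to compare continuous variables". The other endpoints get chi-square, Fisher and log-rank tests. No covariate adjustment, stratified analysis or paired analysis is planned for any of them.

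Section 5.1 (PCI procedure and medication) leaves the strategy of the intervention, the balloon size and the stent to the operator. It does not say whether the choice between cutting and NC balloon falls inside that freedom.

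**The concern.** How patients reach each group decides what the primary comparison means. Under random allocation, an unadjusted difference in minimal stent CSA is free of systematic confounding. Under non-random allocation, the same difference may mix the effect of the balloon with differences in the vessels and lesions treated, and it can be reported only as an association. A reader of this plan cannot tell which applies, and the planned tests are safe from confounding under only one reading.

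Eligibility leaves room for the groups to differ. Section 7.1 admits reference vessels from 2.0 to 4.0 mm, any calcium arc from 100 degrees upward, and both de novo lesions and in-stent restenosis.

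**Working it through.** The plan has no figure of its own on this point. The check compares the texts and then asks whether the endpoint depends on a characteristic that could differ between groups.

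**1. How many conflicts?** *Observational* and *matched cohort* agree with each other. *Randomized* agrees with neither. So there is one two-way conflict, random against non-random allocation.

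**2. Does other text settle it?**
- *Assigned* in section 4.1 suggests allocation by the study, but it stands in the same sentence as the matched-cohort label.
- Intention-to-treat and unpaired tests in section 4.2 suit a randomised trial, but neither establishes one.
- Equal groups of 125 in section 4.3 fit both 1:1 randomisation and 1:1 matching.
- The operator's freedom in section 5.1 is worded too generally to place the choice of balloon group inside or outside it.

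None of these resolves the conflict.

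**3. What do the section 4.2 tests deliver under each reading?**
- *Random allocation:* the unadjusted comparison is acceptable.
- *Non-random, well-matched pairs:* ignoring the pairing mainly costs precision. With within-pair correlation ρ, the unpaired interval is wider than the paired one by the factor 1/√(1 − ρ). The document gives no ρ. Assuming 0.2 gives 1/√0.8 = 1.12, and assuming 0.5 gives 1/√0.5 = 1.41, so the interval is 12% to 41% too wide.
- *Non-random, matching absent or inadequate:* the remaining confounding is not corrected.

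**4. Does the endpoint depend on vessel size?** Inputs:
- stent expansion e = minimum stent CSA / reference lumen CSA (section 5.3, IVUS procedure and analysis);
- e = 0.8, the cut-off for under-expansion in the same section;
- reference diameter D from 2.0 to 4.0 mm (section 7.1).

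Assumptions: the reference lumen is a circle, its diameter is the reference vessel diameter of section 7.1, and e is the same at every size. Then stent CSA = e × (π/4) × D².

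- e = 0.8, D = 2.0: 0.8 × 3.14 = 2.51 mm²
- e = 0.8, D = 4.0: 0.8 × 12.57 = 10.05 mm²
- e = 1.0: 3.14 and 12.57 mm²

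The ratio is (4.0/2.0)² = 4 for any common e. Eligible vessels therefore span a fourfold range of stent area at equal expansion.

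**5. Does this give the size of a bias?** No. A bias also needs an imbalance in vessel size between the groups, and the document reports none. Step 4 shows that the endpoint is sensitive to vessel size, and no more.

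**The case against.** The strongest reply is that the trial is probably randomised and only badly labelled. The opening line says so, patients are assigned 1:1, and the analysis is the standard one for a randomised trial. On that reading the unadjusted tests are acceptable. This stands as far as it goes: harm from confounding is conditional and has not been shown. But it does not remove the point. Even then, two labels are wrong and the allocation procedure is missing.

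A reader might infer three stronger claims, which the document does not support.

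- *That confounding is left wholly uncontrolled.* Matching is itself control at the design stage, and section 4.1 says the cohort is matched. What is missing is the matching variables and an adjusted analysis.
- *That operators choose the balloon group.* Section 5.1 does not say this. Its wording is open, which calls for clarification and is not evidence of selection.
- *That the possible bias can be sized against the cited earlier study.* Section 4.1 reports that "the mean CSA after cutting balloon treatment for native coronary artery disease are 6.26mm and 5.03 mm in the NC balloon group", a difference of 6.26 − 5.03 = 1.23. Setting a vessel-size shift against 1.23 would need an assumed imbalance and an assumed expansion. It would also compare different things if the cited mean CSA is not minimum stent CSA, and the plan does not say that it is. No such comparison is made here.

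**Conclusion.** The point holds and must be fixed. It rests on the contradiction in the current text and on the missing description of allocation or matching, not on demonstrated bias. The planned unpaired, unadjusted tests are sound if allocation is random. If it is not, they leave whatever confounding the unspecified matching fails to remove, and the conclusion can be only an association.

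The area range of about 2.5 to 10.1 mm² shows why vessel size could matter. It depends on a circular reference and a constant expansion of 0.8. It does not estimate a bias, and no error rate is claimed: a false-noninferiority rate would need a margin, and the document states none.

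**What to change.** State one design, in the same words in sections 1 and 4.1.

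*If allocation is random:* delete *observational* and *matched comparative cohort*. Describe the concealed 1:1 allocation. State that the cutting or NC balloon group follows that allocation and is not part of the operator's discretion in section 5.1.

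*If allocation is not random:* delete *randomized*. Name the matching variables if patients are matched. In section 4.2, replace the unadjusted primary test with a regression or pair-respecting analysis adjusted for baseline reference vessel diameter, baseline calcium arc and length, in-stent restenosis versus de novo lesion, and site. Limit the conclusion to an association.

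The adjustment variables need no new procedure. Section 5.2 (Quantitative coronary angiography) supplies the diameter: "Coronary angiography will be digitally recorded at baseline and immediately after the procedure", and "The interpolated reference diameter will be considered as the reference segment diameter". Section 5.3 plans IVUS before pre-dilatation and lists calcium arc and length among its measurements. Lesion type follows from the eligibility check, and site is known. If patients are matched on other variables, the sponsor should confirm that these are recorded.

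The cost is wording in sections 1, 4.1, 4.2 and 5.1 and, on the non-random route, one further model and a more modest conclusion. Turning a non-randomised study into a randomised one is not requested.

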5.1. Primary endpoint: the efficacy of cutting balloon

- ① Minimal stent CSA (cross-section area) with IVUS at calcium site

5.2. Secondary endpoint: comparing the clinical outcomes

- ① MACE (major adverse cardiac events): composite of death, MI, TVR at 1yr follow-up
- ② TLR (target lesion revascularization) at 1yr follow-up
- ③ Procedure time, the total amount of contrast, and the number of balloons

3. Analysis plan

- 6.1. Study period: 24 months
- 6.2. Enrollment: 12 months
- 6.3. Follow-up: 12 months
- 6.4. Analysis and result report: 2 months

4. Sample size calculation for the primary analysis

4.1. Hypothesis:

This trial is a 1:1 matched comparative cohort clinical trial, with patients being assigned to either the cutting balloon or the NC balloon group (1: 1 ratio) during the study period. It will test the noninferiority of a strategy of cutting balloon pre-dilatation compared with NC balloon pre-dilatation in the treatment of calcified coronary lesion. minimal CSA at the calcium site assessed by IVUS is the primary endpoint. Limited similar clinical trials on cutting balloon for the treatment of de novo various degree calcified coronary lesions have achieved differing results. The result of a previous study that investigates the efficacy of cutting balloon indicates that the mean CSA after cutting balloon treatment for native coronary artery disease are 6.26mm and 5.03 mm in the NC balloon group (18). We hypothesize that stent implantation after the cutting balloon pre-dilatation will not be inferior to pre-dilatation with NC balloon for the treatment of de novo calcified coronary lesions. Using double-sided inspection, $\alpha = 0.05$ and $\beta = 0.2$, and considering the expected loss to follow-up of 20%, the number of cases to be included should be at least 250. Therefore, we aim for 125 cases for each group. Nevertheless, the sample size proposed was 250 patients in each group to further increase the power and account for possible protocol deviation.

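### The stated aim is noninferiority, but the plan has no margin or decision rule and its only primary test is one of no difference

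*Combined protocol and SAP*

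**What the plan says.** Noninferiority is stated three times. Section 1 (Study protocol) says the trial "will investigate the noninferiority of cutting balloon pre-dilatation compared with NC-balloon pre-dilatation". Section 4.1 (Hypothesis) says "It will test the noninferiority of a strategy of cutting balloon pre-dilatation compared with NC balloon pre-dilatation", and later: "We hypothesize that stent implantation after the cutting balloon pre-dilatation will not be inferior to pre-dilatation with NC balloon". The primary endpoint, under Study Outcomes, is "Minimal stent CSA (cross-section area) with IVUS at calcium site", a continuous measure on which larger is better.

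The analysis of that endpoint is covered only by a general sentence in section 4.2 (Assumption): the "t-test and Mann-Whitney U test will be used to compare continuous variables". Significance is p<0.05, and intention-to-treat is the only analysis set named.

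For sample size, section 4.1 cites an earlier study in which "the mean CSA after cutting balloon treatment for native coronary artery disease are 6.26mm and 5.03 mm in the NC balloon group". With two-sided alpha 0.05 and beta 0.2 it concludes: "considering the expected loss to follow-up of 20%, the number of cases to be included should be at least 250". Section 4.3 confirms 250 in total, 125 per arm, although section 4.1 also mentions 250 per group. No section gives a margin, an SD, or a confidence-limit rule.

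**The concern.** A noninferiority hypothesis has no content until the tolerable deficit is fixed. Without a margin, no analysis can test it. The t-test and Mann-Whitney test address a different null hypothesis, that of no difference, and failing to reject that null does not show that a deficit is small.

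If the plan is followed exactly, the one result that supports the claim is significant superiority of the cutting balloon, which implies noninferiority at any margin. A non-significant result has no pre-specified meaning for the claim. Nor does a small significant deficit, which might lie within a margin nobody has stated. In practice the risk is that p>0.05 is reported as showing noninferiority, or that a margin is chosen once the data are known. The documents plan neither, but they exclude neither.

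**Working it through.** **Inputs from the documents.** Prior means 6.26 and 5.03, difference 1.23 in favour of the cutting balloon (printed in mm, read here as mm²); two-sided alpha 0.05; 80% power; 20% loss; 125 per arm, so 125 × 0.8 = 100 evaluable.

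**Assumed.** The SD, because none is given. I use 3.1, 2.0 and 1.5 mm². The value 3.1 is solved from the plan's own total in step 1; the other two are illustrative.

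**Step 1. The plan's 250.** For a two-sided test of a 1.23 difference with 100 per arm, the implied SD is 1.23 × √(100/2) / (1.960 + 0.842) = 3.10. So 250 matches a difference test only at an SD of about 3.1. At SD 2.0 the same formula gives 42 per arm, or 53 after 20% loss (106 in total). Read as a noninferiority design, many pairs of margin and SD fit: margin 1.0 with SD 2.5, for example, gives 99 per arm, or 124 after loss. No margin can be inferred from 250, and 250 can be neither confirmed nor refuted.

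**Step 2. True equality.** A two-sided 5% test puts 2.5% in each tail, so P(significantly better) = 0.025 for any SD and any n.

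**Step 3. How often a true deficit gives p>0.05.** SE = SD × √(2/n), power from the noncentral t. The 125-per-arm columns are relevant because "IVUS will be performed at baseline (before pre-dilatation) and repeated immediately after stent implantation in all cases" (section 5.3), so losses over the following year need not remove the primary endpoint.

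| SD | 100/arm: deficit 0.5 | 0.75 | 1.0 | 125/arm: deficit 0.5 | 0.75 | 1.0 |
|---|---|---|---|---|---|---|
| 3.1 | 79% | 60% | 38% | 75% | 52% | 28% |
| 2.0 | 58% | 25% | 6% | 50% | 16% | 2% |
| 1.5 | 35% | 6% | 0.3% | 25% | 2% | <0.1% |

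**Step 4. What margin the trial could support.** The smallest margin with 80% power at true equality is (1.960 + 0.842) × SE. For SD 2.0 and n = 100, this is 2.802 × 0.283 = 0.79 mm².

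| Evaluable per arm | SD 3.1 | SD 2.0 | SD 1.5 |
|---|---|---|---|
| 100 | 1.23 | 0.79 | 0.59 |
| 125 | 1.10 | 0.71 | 0.53 |
| 250 (the per-group figure in section 4.1) | 0.78 | 0.50 | 0.38 |

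The 1.23 in the first cell is not independent support for the design: 3.1 was solved from that same difference and the same 100 per arm.

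**The case against.** The only effect in the documents is a benefit of 1.23. If it is real, the planned t-test with 100 per arm is significant in favour of the cutting balloon in 80%, 99% and more than 99.9% of trials at SDs of 3.1, 2.0 and 1.5 (88%, 99.8% and more than 99.9% with 125 per arm), and noninferiority follows. On this view the authors mean superiority and the gap rarely matters. It can also be said that the 2.5% presumes a rule the plan never states, namely that only a significant benefit counts, and that the SD-dependent figures rest on assumed values.

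Much of this is fair, but it does not remove the defect. The power under a 1.23 benefit belongs beside the less favourable scenarios. Yet a noninferiority design must also work when that benefit is absent or smaller, and section 4.1 itself says that similar trials have given differing results. If superiority is intended, the hypothesis should say so. The 2.5% does depend on using the planned two-sided test as the route to the claim, but the documents offer no other route. The SD-dependent figures are illustrations, and the conclusion does not need them.

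**Conclusion.** The concern holds and must be fixed before analysis. Noninferiority is the stated primary hypothesis, no margin or decision rule exists, and the planned tests address a different question. Two parts of this need no SD: a non-significant result cannot support the claim, and at true equality the planned test supports it in 2.5% of trials. The chance that a real deficit passes as non-significant depends on the SD. For 0.5 mm² it runs from 25% (SD 1.5, 125 per arm) to 79% (SD 3.1, 100 per arm). The gap matters little if the full 1.23 benefit is real, and most if the balloons are similar or the cutting balloon is somewhat worse. The 250 and the 80% power cannot be tied to a noninferiority test.

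**What to change.** Choose one of two routes before any analysis.

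- **Superiority.** Restate the primary hypothesis as superiority in minimal stent CSA, which matches the planned tests. This changes the hypothesis itself as well as its wording, and the sample-size section still needs a stated SD so that 250 can be reproduced. It needs no extra patients unless that SD exceeds about 3.1 (with the 20% loss allowance).
- **Noninferiority.** Pre-specify and justify a margin M in mm² and an SD. Declare noninferiority only if the lower limit of the two-sided 95% confidence interval for cutting minus NC lies above −M. Add a supportive per-protocol analysis beside intention-to-treat. Restate the power at M for a true difference of 0. Allow superiority to be tested from the same interval.

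Under either route, state that p>0.05 will not be taken as evidence of noninferiority, and settle whether the total is 250 or 250 per group.

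The analysis cost of the second route is small: a margin justification, one interval and one supportive run. The sample-size cost depends on M. At an assumed SD of 2.0 and M = 0.5, the requirement is 2 × (2.0 × 2.802 / 0.5)² = 252 evaluable per arm. That is 504 in total if the immediate post-stent image is obtained in everyone, or 252 / 0.8 = 315 per arm and 630 in total with the plan's 20% loss. A wider margin would need fewer.

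### Section 4.1 declares noninferiority only, but the cited effect, the two-sided sizing and the planned test fit superiority, and neither conclusion has a pre-specified rule

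*Combined protocol and SAP*

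**What the plan says.** The combined protocol and SAP states its aim in section 1 and again in section 4.1 (Hypothesis), both times as noninferiority. Section 4.1 says: "It will test the noninferiority of a strategy of cutting balloon pre-dilatation compared with NC balloon pre-dilatation", and then "We hypothesize that stent implantation after the cutting balloon pre-dilatation will not be inferior to pre-dilatation with NC balloon". No section words a superiority hypothesis or an order of testing.

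The surrounding material points elsewhere:

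- The outcomes section heads the endpoint "Primary endpoint: the efficacy of cutting balloon" and defines it as "Minimal stent CSA (cross-section area) with IVUS at calcium site".
- The only numerical basis in section 4.1 is one earlier study, in which "mean CSA after cutting balloon treatment for native coronary artery disease are 6.26mm and 5.03 mm in the NC balloon group".
- The sample size in section 4.1 begins "Using double-sided inspection", with α = 0.05, β = 0.2 and 20% loss to follow-up. It gives neither a margin nor an SD.
- Section 4.2 compares continuous variables by unpaired t-test and Mann-Whitney test, with p < 0.05 as the criterion.

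Section 4.1 arrives at 125 per group but then proposes 250 per group. Section 4.3 gives 125 per group.

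**The concern.** The declared hypothesis and the planned test do not answer the same question. A noninferiority conclusion compares a confidence limit with a margin, and the plan has neither a margin nor such a rule. A non-significant t-test does not show that the cutting balloon is not worse. A significant one in its favour would imply that it is not worse, but only by way of a superiority result to which the plan gives no formal status. The t-test in section 4.2 is a general rule that also covers procedure time and contrast volume. It is not tied to a primary hypothesis.

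At stake is what the trial may formally conclude. If the minimal stent area proves clearly larger with the cutting balloon, a reader can object that superiority was never the stated hypothesis. If the areas are similar, the plan has no rule by which to declare noninferiority.

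**Working it through.** **Inputs from the plan.** Means 6.26 and 5.03, two-sided α = 0.05, β = 0.2, 20% loss and 125 per group (sections 4.1 and 4.3). The difference is 6.26 − 5.03 = 1.23, and 1.23/5.03 = 24%. Evaluable patients per arm: 125 × 0.8 = 100. With 250 per group: 250 × 0.8 = 200.

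**Assumed.** The SD is not stated, so 2.0 to 4.0 mm² is used. The margin is not stated, so the values below are illustrations only.

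**Can 250 be reproduced?** Not from the stated inputs alone. Solving backwards under two designs:

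- Superiority at 1.23: SD = 1.23 / [(1.960 + 0.842) × √(2/100)] = 1.23 / 0.396 = 3.10. An SD of 3.1 gives 100 per arm, 100/0.8 = 125, total 250.
- Noninferiority with no true difference, one-sided 0.025, SD 3.1 and margin 1.23: also 100 per arm and 250 in total. Margin 1.0 with SD 2.5 gives 248.

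The stated total therefore does not reveal which design was sized.

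**Superiority power.** Power = Φ(Δ / [SD × √(2/n)] − 1.960). For Δ = 1.23, SD = 3.1, n = 100: 1.23/0.438 = 2.806, less 1.960 = 0.846, and Φ = 80%.

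| True difference | Evaluable per arm | SD 2.0 | SD 2.5 | SD 3.1 | SD 3.5 | SD 4.0 |
|---|---|---|---|---|---|---|
| 1.23 | 100 | 99% | 94% | 80% | 70% | 58% |
| 1.23 | 125 | >99% | 97% | 88% | 79% | 68% |
| 1.23 | 200 | >99% | >99% | 98% | 94% | 87% |
| 0.615 (half) | 100 | 58% | 41% | 29% | 24% | 19% |

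The 80% at SD 3.1 is circular as evidence, because that SD was obtained by assuming 80% power. The other columns show how far the answer depends on it. The row for 125 is relevant because IVUS is repeated immediately after stenting (Methods, IVUS procedure and analysis), so one-year loss to follow-up should remove few primary values.

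**Noninferiority power.** With margin M, power = Φ((1.23 + M) / [SD × √(2/n)] − 1.960). At SD 3.1 and 100 per arm this is 92%, 98% and 99.9% for M = 0.25, 0.5 and 1.0. If the cited effect were true, noninferiority would be likely and would say little about efficacy.

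**Noninferiority sample size.** At SD 3.1, including 20% loss, the total depends heavily on the assumed true difference:

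| Margin | True difference 1.23 | True difference 0 |
|---|---|---|
| 0.5 | 128 | 1510 |
| 1.0 | 78 | 378 |

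**The case against.** The strongest reply is that superiority is already covered. There is one primary endpoint, section 4.2 applies intention-to-treat to all endpoints, and a two-sided test of difference at p < 0.05 is written in advance. This largely stands. A reader might infer that the trial gives up a superiority conclusion, and the documents do not support that, since the test is planned. What is missing is any statement that a significant result on this endpoint is a superiority conclusion, and how that relates to the declared noninferiority aim.

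A reader might also infer that noninferiority was chosen at no saving in sample size. Without a margin and an SD this cannot be shown, because 250 fits both designs above.

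Nor do the documents show that superiority is within reach. The 1.23 comes from one study of native coronary disease, described as mean CSA, whereas the endpoint here is minimal stent CSA at the calcium site and in-stent restenosis is eligible. Section 4.1 itself warns: "Limited similar clinical trials on cutting balloon for the treatment of de novo various degree calcified coronary lesions have achieved differing results". That is a fair reason for a cautious primary aim. It is not a reason against a second step, since noninferiority would still be tested first and would stand if superiority failed.

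Finally, the sequence cannot run without a margin, so this point cannot be repaired separately from that omission. This is correct, and the fix includes the margin.

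**Conclusion.** The concern holds as a mismatch. The hypothesis is noninferiority without a margin, while the cited effect, the two-sided sizing and the planned test all fit a question of difference. The plan pre-specifies a rule for neither conclusion.

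How likely a superiority conclusion would be is conditional. With 100 evaluable per arm, power reaches 80% only if the true difference is 1.23 and the SD is at most about 3.10. A larger SD or a smaller effect takes it well below that. These figures rest on the normal approximation, a common SD in both arms and the reading of the printed mm as mm².

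The omission does not invalidate the trial, but it should be corrected before outcome data are seen.

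**What to change.** In sections 4.1 and 4.2:

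1. State the noninferiority margin with its justification, and the assumed SD with its source. Correct the unit of the cited areas if mm² is meant.
2. Add a decision rule, for example: *The two-sided 95% confidence interval for the difference in mean minimal stent CSA (cutting minus NC) is used in a fixed sequence. Noninferiority is concluded if the lower limit lies above minus the margin. Only then is superiority concluded, if the lower limit exceeds 0. No alpha adjustment is made.*
3. Reconcile 125 and 250 per group. For the resulting number, report noninferiority power, and superiority power over a range of SDs and for an effect smaller than 1.23.

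The superiority step costs a few sentences and needs no alpha, patients or new data. Stating the margin takes more work. It needs a justification, and it may show that 250 in total is too few if no true difference is assumed (378 at SD 3.1 and margin 1.0).
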